1.2 Primary Objectives

1.1.1 Primary clinical objective:

Identify baseline clinical characteristics and treatment strategies in patients with AIDS-associated primary effusion lymphoma (PEL) that correlate with long-term survival (≥ 2 years).

1.1.2 Primary genomic objective:

Identify differentially expressed genes in PEL that are associated with long-term survival (≥ 2 years).

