2.0 BACKGROUND

2.1 Study Disease

Primary effusion lymphoma (PEL) is a rare type of non-Hodgkin lymphoma (NHL) that presents with predominately body cavity involvement and is nearly universally associated with Kaposi's sarcoma herpesvirus (KSHV), with Epstein Barr virus (EBV) also present in a fraction of cases¹. PEL is typically associated with a poor prognosis with a median survival of 6 months². A solid variant has also been described and carries a similarly poor prognosis³. PEL typically arises in the context of HIV infection, where it accounts for approximately 2-3% of AIDS-NHL².

Data supporting optimal treatment strategies of PEL are limited given the rarity of the disease. There are rare reports of remissions in PEL occurring with the introduction of HAART therapy in HIV patients, who are not on highly active antiretroviral therapy (HAART) at the time of diagnosis. However, HAART is not sufficient for adequate treatment in the vast majority of AIDS-PEL cases. Therefore, combined chemotherapy regimens and other anti-viral treatments are now routinely used for AIDS-PEL treatment. In addition to classic CHOP-based chemotherapy, clinicians and investigators have employed one or more of the following: (a) infusional chemotherapy regimens (EPOCH); (b) methotrexate (after chemotherapeutic debulking or drainage of effusions); (c) VEGF inhibition, aggressive effusion drainage; (d) taken advantage of latent gamma herpes virus tumor infection using bortezomib as an inducer of lytic viral replication and an inhibitor of $NF-kB^4$; and (e) cidofovir or valganciclovir as inhibitors of KSHV replication, with or without interferon⁵. Auto- and allo-geneic hematopoietic stem cell transplant is also reported in the salvage setting with variable success. Long-term AIDS-PEL survivors have been reported², some of whom are being followed at UCSD as well as by collaborators at other institutions within the AMC.

Most of the literature on AIDS-PEL is in the form of single or small case reports, with the largest series including 28 participants reported from a French cohort in 2005^2 . This series explored baseline clinical factors associated with poor survival and identified ECOG performance status > 2 and lack of HAART use at time of diagnosis as independent predictors of shorter survival. A recent review of case in the literature identified the number of body cavity sites as predictive of survival⁶.

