3.0 PARTICIPANT SELECTION

Protocol participants must meet all stated eligibility criteria. A rostered AMC investigator must document that each protocol participant meets all stated eligibility criteria Participating sites must have documentation that each eligibility requirement is satisfied prior to participant enrollment. In compliance with CTEP policy, no exceptions to eligibility criteria will be granted in any circumstance.

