3.1 Eligibility Criteria

Patients diagnosed with primary effusion lymphoma (HIV seropositive or negative) on or after January 1, 1998 on whom survival status at 2 years post PEL diagnosis is available.

Participants may be enrolled to *either or both* the clinical or genomic portions of the study.

The minimum data required to be able to include a participant for analysis of **clinical prognostic factors** are:

- a. HIV status, and for HIV-positive participants, include CD4 count, HIV viral load within one year prior PEL diagnosis (or within 3 months after PEL diagnosis)
- b. Age at PEL diagnosis
- c. Gender
- d. Stage at PEL diagnosis
- e. Treatment of PEL
- f. Response to PEL treatment
- g. Survival status at 2 years post diagnosis
- h. Pathology slides (or paraffin block) for central review
- i. Year of PEL diagnosis

The minimum data required to be able to include a participant for analysis of **genomic prognostic factors** are:

- a. Availability of a pathologic specimen of PEL that will be submitted for genomic analysis
- b. Survival status at 2 years post diagnosis

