3.2 Exclusion Criteria

Patients who do not fulfill the criteria as listed in Section 3.1 above are ineligible.

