4.2 Study Plan

- 4.2.1 Data, Documents, Records, or Specimen Identification:
 - 4.2.1.1 The following data will be collected for participants enrolled into the clinical portion of the study:
 - HIV status, and for HIV-positive participants, include CD4 count, HIV viral load within one year prior PEL diagnosis (or within 3 months after PEL diagnosis)
 - Age at PEL diagnosis
 - Gender
 - Stage at PEL diagnosis
 - Treatment of PEL
 - Best response to PEL treatment
 - Survival status at 2 years post diagnosis
 - Pathology slides for central review (See Appendix II for specimen preparation and shipping)
 - Year of PEL diagnosis
 - 4.2.1.2 The following will be collected for participants enrolled into the genomics portion of the study:
 - Pathology slides for central review (if unavailable, paraffin block may be submitted)
 - Pathologic specimen that will be submitted for genomic analysis:
 - Frozen specimens, formalin-fixed and paraffin-embedded (FFPE) demonstrating PEL including cytospins as well as any mass/nodal biopsies are acceptable (See Appendix II for specimen preparation and shipping)
 - Survival status at 2 years post diagnosis
 - 4.2.1.3 The following is a list of additional data that is highly desirable for inclusion whenever available for participants enrolled in either the clinical and/or genomics portion of the study:
 - Race and ethnicity
 - For participants with HIV: HIV treatment history (which HAART drugs has participant received prior to PEL diagnosis, after PEL diagnosis), baseline HIV characteristics (i.e., CD4 count and HIV viral load closest

to time of PEL diagnosis, history of opportunistic infections)

- Presence or history of other human herpesvirus-8 (HHV-8)-related diseases (i.e., Kaposi's sarcoma, Multicentric Castleman's Disease), and other malignancies)
- Lymphoma baseline disease characteristics (immunophenotype, Epstein-Barr virus (EBV) and Kaposi sarcoma herpes virus (KSHV) status, sites of extranodal involvement), and either IPI or data required for calculation of International Prognostic Index (IPI)
- Lymphoma treatment: type, number of treatment regimens, use of therapeutic effusion drainage
- Best response to PEL treatment, best response duration
- Survival status at time of enrollment and duration of survival in months from PEL diagnosis

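### Required CD4 count and viral load may be drawn up to 3 months after diagnosis, so a baseline value can reflect treatment and some early deaths can be excluded

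*Combined protocol and SAP*

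**What the plan says.** Section 3.1 lists, under "The minimum data required to be able to include a participant for analysis of" clinical prognostic factors, HIV status and, for HIV-positive participants, CD4 count and "HIV viral load within one year prior PEL diagnosis (or within 3 months after PEL diagnosis". The natural reading is that the window covers both measurements. Section 4.2.1.1 repeats it.

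The requirement is binding. Section 3.2 begins "Patients who do not fulfill the criteria as listed in" section 3.1 and declares such patients ineligible. Section 3.0 adds that "no exceptions to eligibility criteria will be granted in any circumstance".

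The primary clinical objective in section 1.2 is to "Identify baseline clinical characteristics and treatment strategies in patients with AIDS-associated primary effusion lymphoma (PEL) that correlate with long-term survival" of two years or more. Section 5.1.1 plans Kaplan-Meier estimates and a Cox model on categorised baseline variables, and section 4.2.1.3 counts survival duration from PEL diagnosis. That section's optional list also includes "baseline HIV characteristics (i.e., CD4 count and HIV viral load closest" to diagnosis, without saying whether before or after.

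The protocol does not require the value to precede PEL treatment or HAART, and does not prefer a pre-diagnosis value. Section 5.1.1 mentions no landmark, delayed entry, time-dependent covariate or missing-data method.

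**The concern.** Two separate problems follow from one window.

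- **The covariate.** Time zero is diagnosis, but the covariate may be measured three months later. Section 2.1 describes patients who begin HAART after diagnosis and says combination chemotherapy is routine. A CD4 count or viral load drawn after either has started is partly a result of treatment. Because the same objective also studies treatment strategies, baseline prognosis and treatment effect become mixed.
- **Entry.** An HIV-positive patient with no value in the year before diagnosis can qualify only through a draw at or after diagnosis. If death comes first, the patient is ineligible for the clinical portion. Patients without recent HIV care are plausibly the ones who lack a prior value (an inference, not a statement in the protocol). Section 2.1 reports lack of HAART at diagnosis as an independent predictor of shorter survival. The rule may therefore thin out early deaths in a high-risk group.

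The accepted period after diagnosis is half the "median survival of 6 months" given in section 2.1, so the timing is not negligible for this disease.

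**Working it through.** The plan states no figure for this point, so there is nothing to reproduce. The steps below only illustrate the size.

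**Inputs.** Median survival is 6 months (section 2.1). The window closes 3 months after diagnosis (section 3.1). Expected two-year survivors are 15-25% (section 5.2) or 25-40% (section 4.3.1). The share f of HIV-positive patients with no value in the prior year is not given; 20-40% is assumed. Draw times are not given; two cases are used, uniform over 0-3 months and all at month 3.

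**Step 1: deaths within the window, exponential curve (assumption).** S(t) = 2^(-t/6), so S(3) = 2^(-0.5) = 0.707 and 29% die by month 3.

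**Step 2: chance of dying before the draw, for a patient with no prior value.**
- Draw at month 3: 1 - 0.707 = 0.293.
- Uniform draw time: the mean of S over 0-3 months is 0.293 / (ln 2 × 0.5) = 0.293 / 0.347 = 0.845, so the chance is 0.155.

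**Step 3: share of HIV-positive cases excluded by this item** = f × chance of dying before the draw.

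| f | Uniform draw | Draw at month 3 |
|---|---|---|
| 0 | 0 | 0 |
| 20% | 3.1% | 5.9% |
| 40% | 6.2% | 11.7% |

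**Step 4: sensitivity to the curve.** The exponential curve implies 2^(-4) = 6% alive at two years, below both expected ranges. Weibull curves that keep the 6-month median, S(t) = exp(-ln 2 × (t/6)^k), can be made to pass through 15%, 25% or 40% at two years. For 25%, k = 0.5 and S(3) = exp(-0.693 × 0.707) = 0.613. The three curves give 34%, 39% and 45% dead by month 3. Their mean survival over 0-3 months is 0.790, 0.726 and 0.608. With f = 20-40%, the excluded share runs from 0.20 × 0.210 = 4% to 0.40 × 0.453 = 18%.

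**Step 5: effect on two-year survival.** Everyone excluded this way died within 3 months, so apparent two-year survival = true value / (1 - excluded share). Take 25% true survival and the matching Weibull curve:
- f = 20%: 0.25 / 0.945 = 26% (uniform) or 0.25 / 0.923 = 27% (month 3).
- f = 40%: 0.25 / 0.890 = 28% or 0.25 / 0.845 = 30%.
- Within the group that has only post-diagnosis values: 0.25 / 0.726 = 34% or 0.25 / 0.613 = 41%.

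The effect on the CD4 and viral load associations was not computed; it would need their joint distribution with survival and treatment timing.

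**The case against.** Section 3.1 never calls the window value baseline. The only text that does so for CD4 count and viral load is the optional item in section 4.2.1.3, and asking there for the value nearest diagnosis is a partial safeguard. That is fair, but nearest has no direction and does not exclude a draw after treatment began. Nor does the plan say which value enters the model.

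A post-diagnosis value is allowed, not required, and a draw on the day of diagnosis qualifies. Selection therefore arises only for patients with no prior value who die before any draw. HIV-negative patients are unaffected, and the genomic portion does not need these measurements. All of this stands and limits the scope.

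A reader might infer that about 5 to 9 of the 80 participants would be lost, from 80 × 0.20 × 0.293 = 4.7 and 80 × 0.40 × 0.293 = 9.4. The documents do not support that count. It puts every draw at month 3 and takes every patient as HIV-positive. It uses an unstated share, and it counts excluded cases inside the 80 enrolled, when they would lie outside. Uniform draws alone give 80 × 0.20 × 0.155 = 2.5 to 80 × 0.40 × 0.155 = 5.0.

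A reader might also infer that relaxing item a keeps every such patient. Item f of the same list requires response to treatment, and a patient who dies before a blood draw may lack that too.

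Finally, a shift from 25% to 26-30% is small beside sampling error: with 80 patients the 95% half-width is 1.96 × √(0.25 × 0.75 / 80) = 9.5 points. True, but the bias is concentrated in one subgroup (34-41% against 25%), and it bears on the very factors the objective asks about.

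**Conclusion.** The point holds in a limited form. The rule admits CD4 and viral load values drawn after treatment into an analysis of baseline factors. For HIV-positive patients with no value in the prior year, it can exclude those who die before a draw. That can bias survival estimates upward and distort the CD4 and viral load associations.

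Under the exponential curve and f = 20-40%, about 3-12% of HIV-positive cases would be excluded by this item, with some overlap with item f. The Weibull curves widen this to 4-18%. If every HIV-positive patient has a prior value, there is no selection, although post-treatment values could still be used. The share without a prior value, the draw times and the survival curve are all assumptions, so the documents establish the mechanism but not its size. A design change is worth making because it is cheap.

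**What to change.** - Keep the collection window. Record each draw date alongside the dates of first PEL treatment and HAART start. Section 7.1 already foresees collecting treatment dates. The case report form is not in the documents, so draw dates may already be captured.
- Define the analysis baseline as the last in-window value on or before the first PEL treatment or post-diagnosis HAART start, whichever is earlier. Flag later values and use them only in a sensitivity analysis.
- Do not make a case ineligible for the clinical portion solely because no CD4 count or viral load exists. Keep it in the survival estimates and handle the covariate as missing, with a missing category or with imputation that includes the survival outcome.
- Values absent because of early death may not be missing at random. Add a 3-month landmark or delayed-entry sensitivity analysis.
- Report how many HIV-positive cases have a pre-treatment value, only a later value, or none.

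The cost is some missing CD4 and viral load values and a little more analysis work. Cases lacking other minimum data, such as item f, would still be excluded.

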1.1 Hypothesis

We hypothesize that there will be a sub-set of PEL clinical characteristics and differentially expressed genes in PEL cells that will be predictive of long-term survival (≥ 2 years), when data from long-term and short-term survivors of the disease are compared.

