4.3 Genomics Methods

4.3.1 RNA Extraction and Quality Assessment

The vast majority of specimens are in the form of archived blocks of cells prepared from cytospin of PEL fluid that are formalin-fixed and paraffin-embedded (FFPE). Each specimen will be centrally reviewed for morphology and immunophenotype to confirm the diagnosis of PEL and to ascertain the percentage of tumor cells in the tissue block. Only samples containing > 95% PEL cells will be further profiled. It should be noted that PEL effusions are typically quite homogeneous, such that all 9 of the specimens assessed by Klein et al. met this criteria⁷. Thus, we expect that nearly all of the FFPE PEL specimens received for this study should be able to move forward for expression profiling. Based on our experience and feedback from outside AMC investigators, we expect that 25-40% of the PEL samples will be from patients who are long-term survivors (20-32 of the 80 total PEL specimens).

Total RNA will be extracted from FFPE PEL sections using a method that enables preparation of RNA for use in both microarray and RNA-Seq assay protocols (i.e., Prelude FFPE Isolation Module (NuGen Inc.)). Some 5 x 20 micron sections of the trimmed FFPE blocks will be extracted by column purification following deparaffinization and lysate preparation. RNA quantity will be measured by OD 260/280/320 assay on a NanoDrop spectrophotometer. Although we anticipate the RNA to be variably degraded, we will still assess its quality by determining a RIN score following Bioanalyzer assay. This will permit us to determine whether a very poor RIN metric (i.e., < 7) was instrumental in the outcome of an expression assay and enable better comparison of the results. We will use enough of each PEL specimen to prepare approximately 400 ng of total RNA. The RNA will be stored at -80°C.

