APPENDIX II: SPECIMEN PREPARATION AND SHIPPING INSTRUCTIONS BACKGROUND AND PROCEDURES

The following specimens are required for participation in the genomics portion of the study:

- Paraffin embedded tissue or cytology block or frozen tissue specimen (latter preferred if available).
- Pathology slides and a pathology report for central pathology review. If slides are not available, the site must provide a paraffin block for review, which if adequate, will also be used for genomic studies. The participant can be included in the clinical portion of the trial if the material submitted is only sufficient for pathology review.
- If neither slides nor adequate paraffin block is available, the participant will be considered ineligible.

For participants in the clinical portion, pathology slides and a pathology report are required for central pathology review.

Slides and/or tissue blocks will be returned to the site once all studies are complete.

Details regarding specimen shipment are provided in the protocol Manual of Procedures.

Technical questions regarding tissue specimens should be directed to [name] (see Protocol Roster).

The AMC Biorepository will ship pathology slides and tissue specimens to UCSD and Cornell for central pathology review. Specimens for genomic analysis will be sent to UCSD.

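### The genomic specimen rules set no sampling time, so post-treatment or relapse material can enter the survivor comparison unrecorded

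*Combined protocol and SAP*

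**What the plan says.** The hypothesis (section 1.1) is about prediction: it expects "differentially expressed genes in PEL cells that will be predictive of long-term survival", with survival counted from diagnosis and long-term meaning at least 2 years. The genomic objective in section 1.2 speaks of association with that outcome.

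The rules for the genomic specimen are:

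- **Section 3.1, genomic item a:** "Availability of a pathologic specimen of PEL that will be submitted for genomic analysis". The only other minimum item is "Survival status at 2 years post diagnosis".
- **Section 4.2.1.2:** frozen or FFPE material "demonstrating PEL including cytospins as well as any mass/nodal biopsies are acceptable".
- **Section 4.3.1:** central review confirms the diagnosis, and "Only samples containing > 95% PEL cells will be further profiled".
- **Appendix II:** "Paraffin embedded tissue or cytology block or frozen tissue specimen (latter preferred if available", plus slides and a pathology report for central review.

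Each restricts the specimen by material, diagnosis or purity. None restricts it by time. Other predictors are anchored: section 3.1 asks for CD4 count and "HIV viral load within one year prior PEL diagnosis (or within 3 months after PEL diagnosis", and takes age and stage at diagnosis.

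**The concern.** A predictor of survival from diagnosis should be measured at or near diagnosis. If it can be measured later, the chance of obtaining a late measurement may depend on the outcome. Here a patient who relapses three years after diagnosis could contribute the relapse block under the rules as written, and that patient is a long-term survivor by definition. Expression changes caused by prior chemotherapy, antiviral treatment, HAART or selection at relapse could then separate the two groups without saying anything about prognosis at diagnosis.

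Multiplicity correction does not address this. It limits chance findings, whereas a treatment-induced difference between the groups would be a real difference with the wrong explanation. What is at stake is whether genes from one of the two primary objectives can be called predictive.

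**Working it through.** **1. Is timing controlled anywhere?** The plan states no power, effect size or timing figure for this comparison, so there is nothing of its own to reproduce. The check is of the text.

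- *Entry and specimen rules (3.1, 4.2.1.2, 4.3.1, Appendix II):* no sampling window and no pre-treatment condition. Where a case has several specimens, the only stated preference is for frozen material.
- *Replacement (3.3.3):* only for insufficient specimen or genetic material.
- *Data lists (4.2.1.1 to 4.2.1.3):* no specimen date and no therapy before sampling. Lymphoma treatment type and number of regimens are in 4.2.1.3 for both portions, but as desirable items not tied to the specimen.
- *Analysis (4.3.2.1, 5.1.1):* no adjustment, stratification or sensitivity analysis by specimen timing.

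**2. What follows without assumptions.** A non-long-term survivor has died by 24 months, so every specimen taken after month 24 comes from the long-term group.

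**3. Time alive before 24 months (illustration).** Assume exponential survival with S(24) = s. Then λ = −ln(s)/24. Among those who die before 24 months, mean survival is 1/λ − 24s/(1−s) and median survival is −ln((1+s)/2)/λ. Section 2.1 gives a 6-month median, which implies s = 0.5^(24/6) = 6.25%. The protocol expects more long-term survivors: 25–40% in section 4.3.1 and 15–25% in section 5.2.

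| s | λ | Mean (months) | Median (months) | 24/mean | 24/median |
|---|---|---|---|---|---|
| 6.25% | 0.1155 | 7.06 | 5.48 | 3.4 | 4.4 |
| 15% | 0.0790 | 8.42 | 7.00 | 2.9 | 3.4 |
| 25% | 0.0578 | 9.31 | 8.14 | 2.6 | 2.9 |
| 40% | 0.0382 | 10.19 | 9.34 | 2.4 | 2.6 |

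At the protocol's own expected shares, long-term survivors have at least about 2.4 to 3.4 times as long in which a later specimen could arise. This is time alive, not number of specimens.

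**4. Effect on one non-prognostic gene (illustration).** Two-sided t-test at an unadjusted 5%, with a 2 SD shift in late specimens. The shift and the late shares are assumptions.

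*Fixed numbers of late specimens in the planned 10 v 10 set (long-term v non-long-term):*

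| Late specimens | Rejection rate |
|---|---|
| 0 v 0 | 5% |
| 2 v 0 | 8% |
| 3 v 0 | 14% |
| 4 v 0 | 23% |
| 3 v 1 | 5% |
| 3 v 2 | 1.6% |

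*Late status drawn at random for each specimen:*

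| Late share | 10 v 10 | 20 v 60 |
|---|---|---|
| 20% v 20% | 5% | 5% |
| 20% v 5% | 8% | 19% |
| 30% v 10% | 10% | 25% |
| 40% v 10% | 17% | 46% |

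The 20 v 60 split is 25% of 80. At fixed counts of 3 v 1 the inflation vanishes, partly because the late specimens also widen the within-group variance. With random shares of 30% v 10% it is about twofold at 10 v 10. Equal shares give no inflation. At a threshold of p < 0.001, the 3 v 0 case rejects about 0.3% of the time.

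**The case against.** The strongest reply is that this builds a good deal on silence.

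- **No passage invites late material.** The phrase accepting any mass or nodal biopsy concerns tissue type. Effusion drainage is mentioned, but repeated drainage is not described. A reader might infer that the plan deliberately accepts relapse specimens; the text supports only that it does not exclude them. This stands.
- **Timing may be recoverable.** Appendix II requires a pathology report, which would ordinarily date the specimen (an inference), and section 7.1 lists treatment and response among the dates collected. It would therefore be too strong to say that the problem could never be detected. This stands, but no step requires anyone to extract or use the timing.
- **Direction is uncertain before 24 months.** A survivor in remission yields no PEL specimen, while a patient with refractory disease may be sampled on treatment. A reader might infer that late specimens come only from survivors; that is literally true only after month 24. This stands.
- **The planned test is corrected for multiplicity.** Section 4.3.2.1 specifies Westfall-Young correction and FDR < 0.05, so the unadjusted rates do not show that false genes would be reported from 10 v 10. This stands for that set. Correction does not remove a confounded difference, and section 5.1.1 allows up to 80 specimens, where exposure is greater.
- **The disease is rare.** Mandatory exclusion could threaten the 20-specimen minimum in section 3.3.1. This stands, and it shapes the fix.

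None of these points supplies a timing rule or a timing variable.

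**Conclusion.** The gap is real. The genomic specimen is not fixed in time, its timing is not a listed data item, and no stated analysis uses it. Following the plan can therefore mix diagnostic with post-treatment or relapse material in a comparison meant to find predictive genes.

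The size is unknown, because the documents do not give the share of late specimens in either group. The time-alive ratio of about 2.4 to 3.4 assumes exponential survival and the protocol's 15–40% long-term survivors. The rejection rates depend on assumed shares and shifts. Both are illustrations, not estimates of bias in this study.

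A reader might conclude that the primary genomic objective is defeated. The documents do not support that: many archived specimens may be diagnostic, and dates may be recoverable. The point should be fixed, ideally before specimens are selected.

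**What to change.** 1. Add two fields to the specimen form for every genomic case: specimen collection date, and PEL therapy before specimen (yes/no).
2. In section 3.1 (genomic item a), section 4.2.1.2 and Appendix II, state that where a case has several specimens, the diagnostic pre-treatment one is to be submitted.
3. In sections 4.3.2.1 and 5.1.1, base the primary comparison of long-term with non-long-term survivors on specimens taken at diagnosis before PEL-directed therapy. Report later specimens separately.
4. If that leaves fewer than the 20-specimen minimum, keep the later specimens, report the pre-treatment-only analysis alongside, and limit any claim of prediction to genes that hold in it.

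The cost is a wording change in a few sections and two form fields. The downside is that some cases with only later material may leave the primary comparison; the documents do not say how many.
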